Official title:
**CHARACTERIZATION OF VIETNAMESE PATIENTS WITH OBESITY
AT OUTPATIENT CLINICS**

STUDY PROTOCOL

CHARACTERIZATION OF VIETNAMESE PATIENTS WITH OBESITY AT OUTPATIENT CLINICS

STUDY PROTOCOL

Hypothesis

In the past three decades, obesity has emerged insurmountably, not only in affluent nations but also in many low- and middle-income countries worldwide. It has been linked to various non-communicable diseases, including hypertension, coronary heart disease, diabetes mellitus, dyslipidemia, stroke, colorectal cancer, and many other chronic conditions, such as musculoskeletal disorders, putting tremendous pressure on healthcare systems and the socio-economy.

The Asia and Pacific region harbors the highest absolute number of people with overweight and obese, amounting to approximately 1 billion. In Southeast Asia, the prevalence of overweight and obesity increased by almost 40% between 1990 and 2013. Although Vietnam has the lowest percentage of obese adults in the region (about 3.6%), we experienced a 38% increase in the number of obese people between 2010-2014, much higher than that in the United Kingdom and the United States (10% and 8% correspondingly). However, the problem is underestimated by not only healthcare professionals but also patients with obesity. These alarms underscore the necessity of implementing a comprehensive assessment and more focused and practical strategies for addressing obesity in Vietnam, where data has been limited. This research will be a foundation for further research on obesity in Vietnam and Southeast Asia.

Therefore, our research has two arms: (1) characterization of patients with obesity to identify those at the highest risks for obesity complications, and (2) understating the attitudes and perceptions of people living with obesity to gain insights into the psychological factors associated with obesity. This research will be a foundation for further research on obesity in Vietnam and Southeast Asia.

Objective

- (1) Characterization of patients with obesity to identify those at the highest risks for obesity complications
- (2) Understating the attitudes and perceptions of people living with obesity to gain insights into the psychological factors associated with obesity.

Study design

Study type: Observational

Methods

Recruitment

Morbidly obese subjects attending clinic at University Medical Center Ho Chi Minh City and My Duc General Hospital.

Inclusion criteria

- Men and women
- Above 18 years old
- Being obese (Body mass index - **BMI ≥ 25 kg/m² as per Asia-Pacific Guidelines for Obesity**)

Exclusion criteria

- Not meeting the inclusion criteria
- Pregnancy and post partum
- Inability to cooperate with height measurement.
- Inability to answer questionnaire.

Protocol

A structured questionnaire will be asked by well-trained research staff according to a face-to-face interview. Obtained information includes age, sex, occupation, relationship status, presenting chief complaint, past medical history, family history, current medication, weight loss history, and self-perception about obesity. Questions about weight loss history and self-perception about history are modified from the WALI questionnaire (Weight and Lifestyle Inventory questionnaire), a self-report assessment tool to evaluate factors related to obesity management. Participants will then be assessed for risk of depression using PHQ-9 (Patient Health Questionnaire-9). It is scored on a 27-point scale. Those with a PHQ-9 score less than five is considered at no risk of depression, and those with a PHQ-9 score equal to or more than 5 are at risk of depression.

Blood pressure measurement: All participants will have their blood pressure taken by a standardized sphygmomanometer.

Anthropometric measurements: Anthropometric parameters will be measured at baseline. Measurements include waist circumference, hip circumference, body weight, height, and BMI.

Waist and hip circumference are measured per WHO STEPwise Approach to Surveillance protocol (WHO STEPS, 2008b). Waist circumference is measured at the approximate midpoint between the lower margin of the last palpable rib and the top of the iliac crest. Hip circumference is measured around the widest portion of the buttocks.

Height and weight measurements will be taken using a professional medical HM200P Portable Height Stadiometer and a standardized weight scale (ISO 9001:2015), by professional and experienced physicians. BMI will be computed by the following equation: weight in kilograms divided by height in meters squared.

Bioelectrical impedance analysis (BIA): Electrical bioimpedance (Tanita MC-780 MA; Serial: 17050004) will be used to assess weight and body composition, including: fat mass, muscle mass, fat %, SMM, and visceral fat rating.

Biochemical measurements

Biochemical measurements will be performed at baseline, including plasma glucose, total cholesterol (TC), LDL-cholesterol (LDL-C), HDL-cholesterol (HDL-C), and triglycerides.

All participants will receive nutritional counseling at the end of the survey.

Statistical Analysis Plan:

All the data will be analyzed using STATA version 16.0 software. Parametric tests will be applied for quantitative variables with normal distributions and non-parametric tests for qualitative and quantitative variables with abnormal distributions. The results will be expressed as average \pm standard deviation. Use frequencies and percentages for descriptive statistics. The Chi-square test will be used to evaluate the levels of relevance for comparisons of risk factors and complications of severe obesity. Relevancy was measured by odds ratio (OR) and 95% confidence interval of OR. The statistical analysis to evaluate the gene-diet interaction was a univariate ANCOVA. For continuous variables, comparisons are made with the analytical univariate ANCOVA. A P- value of less than 0.05 was considered significant.

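### Does the protocol reduce the PHQ-9 to a split at 5 and so throw away information about depression?

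*Protocol*

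**What the plan says.** The PHQ-9 appears only under Methods, in the Protocol subsection that describes the interview. The purpose is given first: "Participants will then be assessed for risk of depression using PHQ-9". The scale follows, "It is scored on a 27-point scale", and then the two categories. The lower one is set out thus: "Those with a PHQ-9 score less than five is considered at no risk of depression". For the upper category, the protocol's definition is that "those with a PHQ-9 score equal to or more than 5 are at risk of depression". There are no severity bands and no other cut-off.

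The second item under Objective concerns attitudes and perceptions, in order "to gain insights into the psychological factors associated with obesity".

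The Statistical Analysis Plan section of the protocol opens by covering all the data and then gives general rules. Quantitative variables get parametric tests if normal; otherwise the rule is "non-parametric tests for qualitative and quantitative variables with abnormal distributions". Continuous variables are compared by univariate ANCOVA. Frequencies and percentages are used for description. A chi-square test serves comparisons of risk factors and complications of severe obesity, and "Relevancy was measured by odds ratio (OR) and 95% confidence interval of OR". Neither the PHQ-9 nor depression is mentioned there.

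**The concern.** The split at 5 is the only PHQ-9 rule the protocol writes down. The PHQ-9 is also the one scored psychological scale it names, and an objective is about psychological factors. A two-level classification fits naturally with a chi-square test and an odds ratio, so a reader may infer that this is how depression will be related to other characteristics.

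If so, the cost would be real. Every score from 5 to 27 would count the same, severity above the threshold could not be described, and intervals for associations would be wider than the same participants could give. The label adds to the unease: a 4 is called no risk and a 5 at risk, which is more absolute than a screening score can support.

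**Working it through.** The protocol gives no sample size, effect size, PHQ-9 distribution or expected share at or above 5, so there is no planned figure to reproduce. Two questions can be checked: what the text commits to, and what a split-only analysis would cost.

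**1. What the text commits to**

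- *Where the split stands.* It follows the description of the instrument, in the data-collection text. It says how a participant is classified. It does not say which form of the score enters a test.
- *Whether the total is excluded.* No sentence drops it. It must be obtained before the split can be applied, so it will be in the data.
- *Whether a rule covers the total.* The analysis section applies to all the data and has rules for quantitative variables, both normal and not. A total on a 27-point scale is a quantitative variable.
- *Whether the PHQ-9 is treated differently from other measures.* It is not. BMI, waist, blood pressure, glucose, lipids and body composition are not assigned to a named test either.
- *Whether the chi-square rule claims the PHQ-9.* It does not. That sentence concerns risk factors and complications of severe obesity.

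To reach a split-only analysis, a reader must supply two steps the text does not contain: that associations with the PHQ-9 will be tested, and that only the two categories will be used.

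**2. What a split-only analysis would cost**

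Let p be the share scoring 5 or more (assumed). Efficiency is the information in the split relative to the whole score. Four models:

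- A: normal trait, efficiency = φ(z)²/[p(1−p)], where z cuts off an upper tail of p. At p = 0.2, φ(z) = 0.280, giving 0.0784/0.16 = 0.490. At p = 0.5, 0.1592/0.25 = 0.637.
- B: skewed score (negative binomial truncated to 0–27, shape 0.8, 1.5 or 3) with a latent-normal association.
- C: the same scores under proportional odds, efficiency = 3p(1−p)/(1 − sum of cubed category shares).
- D: the same scores with a shift in the log mean, using Fisher information.

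| p | A | B | C | D |
|---|---|---|---|---|
| 0.1 | 0.342 | 0.377–0.408 | 0.281–0.294 | 0.524–0.616 |
| 0.2 | 0.490 | 0.528–0.553 | 0.492–0.501 | 0.629–0.660 |
| 0.3 | 0.576 | 0.614–0.632 | 0.640–0.645 | 0.642–0.651 |
| 0.4 | 0.622 | 0.660–0.671 | 0.727–0.729 | 0.612–0.631 |
| 0.5 | 0.637 | 0.673–0.679 | 0.755–0.757 | 0.566–0.586 |

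For p from 0.2 to 0.5, efficiency runs from 0.490 to 0.757. The loss is 1 − 0.757 = 24% to 1 − 0.490 = 51%. At p = 0.1 it is 1 − 0.616 = 38% to 1 − 0.281 = 72%.

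In sample-size terms, take an assumed difference of 0.5 SD, two-sided 0.05 and 80% power. The undivided score needs 2(1.960 + 0.842)²/0.5² = 62.8, so 63 per group. Shifting each group by 0.25 SD around the cut gives proportions of 0.401 and 0.599 (p = 0.5) or 0.137 and 0.277 (p = 0.2), and the split needs 100 or 132 per group. With 63 per group the split has about 60% or 49% power.

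**3. What these figures show**

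They describe dichotomising in general. Every input except the 0–27 range, the cut at 5 and the 0.05 level is assumed. All four models also let the effect act along the whole scale, which favours the total; an effect concentrated at the threshold would cost the split less. For the descriptive proportion at or above 5, the split loses nothing, because the split is that proportion.

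**The case for a change.** The best case for the concern has two parts.

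First, the PHQ-9 is not quite like the other measures. BMI has a threshold for eligibility, but the PHQ-9 alone among the measured quantities is turned into two classes for reporting, and those classes lean towards the chi-square and odds-ratio rule. The protocol also carries its own section headed Statistical Analysis Plan, where one sentence could have settled the matter. This part stands only as a description. The lean is an inference, the rules for quantitative variables remain open to the total, and a fuller plan may assign variables to tests. A possible misreading is not a wrong instruction.

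Second, the label is written text, so it does not depend on any unseen document, and calling every score below 5 free of risk is too strong for a questionnaire. As a comment on wording this is fair. But the protocol says such participants are considered to be at no risk, as one half of a pair of category names. Other names would leave the same people in the same groups and give the same proportion and the same test. To show that the cut-off itself is wrong would need a source outside the documents.

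**Conclusion.** The concern does not hold. The protocol classifies the PHQ-9 at 5, keeps the total available, and has general rules that cover a quantitative score. It does not plan a split-only analysis, and the absence of a named test for the PHQ-9 is shared by every other measured variable and is commonly left to a separate analysis plan.

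The 24% to 51% loss of information is sound arithmetic for a split-only analysis with 20% to 50% scoring 5 or more, under effects spread along the scale. It is not a consequence of following this protocol. An instruction to analyse the total as a quantitative variable would largely repeat the existing rule. What remains is a preference for a less absolute category name, which alters no result. This conclusion rests on reading the general analysis rules as applying to the PHQ-9 total, as their wording allows. A later plan that restricted associations to the split would reopen the question.

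### The odds ratios for complications under Objective 1 are planned without adjustment for age or sex, so those for factors related to age or sex can be confounded

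*Protocol*

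**What the plan says.** - **Aim.** The Hypothesis section, repeated under Objective, sets the first arm as "characterization of patients with obesity to identify those at the highest risks for obesity complications".
- **Design and population.** The Study design section gives "Study type: Observational". The inclusion criteria admit both sexes, and on age say only "Above 18 years old".
- **Data.** The section headed Protocol lists the interview items: "Obtained information includes age, sex, occupation, relationship status, presenting chief complaint", followed by history, medication and other items.
- **Analysis of risk factors against complications.** The Statistical Analysis Plan section fixes the method: "The Chi-square test will be used to evaluate the levels of relevance for comparisons of risk factors and complications of severe obesity". The measure follows: "Relevancy was measured by odds ratio (OR) and 95% confidence interval of OR". The decision rule is "A P- value of less than 0.05 was considered significant".
- **The only covariate-type method named.** ANCOVA appears for a gene-diet interaction and then generally: "For continuous variables, comparisons are made with the analytical univariate ANCOVA". No covariate is listed in either place.

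**The concern.** The section assigns a definite method to the comparison that carries Objective 1, and that method is unadjusted. It names no logistic regression, no Mantel-Haenszel stratification and no adjustment set for the ORs. The ANCOVA sentences do not fill the gap, because they concern continuous variables and do not produce ORs for binary complications.

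Nothing in the design balances age or sex between patients with and without a given factor. Where a factor is related to age or sex, and age or sex is related to the complication, the crude OR mixes the factor's own association with that of age or sex. Calling the variables risk factors and applying a 0.05 threshold invites the reader to take each significant OR as a separate marker of risk. A factor that merely tracks age could then be reported as one.

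**Working it through.** The protocol states no sample size, prevalence, event count or OR, so there is no figure of its own to reproduce. The calculations below are illustrations on assumed inputs. In each, the factor has no association of its own with the complication, so the true age-adjusted OR is 1.0.

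**Illustration A: continuous age**

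Assumed inputs: factor held by 40% of patients; age normal with SD 11 within each group; overall complication prevalence 40%; log-odds of the complication linear in age.

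The risk in group g is R(g) = E[expit(a + b × age)], where age has mean 0 in those without the factor and mean equal to the age gap in those with it, and b = ln(age OR per decade)/10. The intercept a is set so that 0.4 × R(with) + 0.6 × R(without) = 0.40. Crude OR = odds of R(with) ÷ odds of R(without).

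| Age gap (years) | Age OR per decade | Risk with factor | Risk without | Crude OR |
|---|---|---|---|---|
| 0 | any | 0.400 | 0.400 | 1.00 |
| any | 1.0 | 0.400 | 0.400 | 1.00 |
| 3 | 1.6 | 0.419 | 0.387 | 1.14 |
| 5 | 1.3 | 0.419 | 0.388 | 1.14 |
| 5 | 1.6 | 0.432 | 0.379 | 1.25 |
| 10 | 1.6 | 0.464 | 0.357 | 1.56 |

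Example, last row: (0.464/0.536) ÷ (0.357/0.643) = 0.866 ÷ 0.555 = 1.56.

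Varying the prevalence from 10 to 60%, or the age SD from 9 to 14, moves the four biased values only within 1.14–1.15, 1.14, 1.24–1.26 and 1.54–1.58. The age gap and the strength of the age effect therefore drive the result.

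Share of simulated studies (4,000 per cell) with p < 0.05, at assumed sample sizes:

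| Gap / age OR | Chi-square, n = 200 | n = 300 | n = 500 | Adjusted SE ÷ crude SE |
|---|---|---|---|---|
| 5 years / 1.3 | 7% | 9% | 11% | 1.04 |
| 5 years / 1.6 | 12% | 14% | 22% | 1.06 |
| 10 years / 1.6 | 32% | 45% | 66% | 1.12 |

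Age-adjusted logistic regression in the same cells rejects in 4 to 5% of studies.

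**Illustration B: two age strata, as a check by a different route**

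Assumed inputs: half the patients older and half younger; 20% complication risk in the younger; age-complication OR 3; factor present in 70% of older and 30% of younger patients.

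- Older risk: odds 0.25 × 3 = 0.75, so the risk is 0.75/1.75 = 0.4286.
- With the factor: complication 0.35 × 0.4286 + 0.15 × 0.20 = 0.180; none 0.500 − 0.180 = 0.320.
- Without it: complication 0.15 × 0.4286 + 0.35 × 0.20 = 0.1343; none 0.500 − 0.1343 = 0.3657.
- Crude OR = (0.180 × 0.3657)/(0.320 × 0.1343) = 1.53, although the OR within each stratum is 1.0.

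With the milder split of 60% and 40%, the crude OR is 1.15 to 1.40 for age-complication ORs of 2 to 6. With 50% and 50% it is 1.00. Both routes give the same pattern: bias when both links are present, none when either is missing.

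**The case against.** **The objective is descriptive.** It asks which patients are at highest risk. A factor that tracks age is still a valid marker for that purpose, and the crude OR estimates the marginal contrast without bias. On that reading the rejection rates above are not type I errors, because the marginal association is real. This stands as far as it goes, and is why the crude ORs should be kept. It does not remove the concern: the crude OR alone cannot separate a marker of risk from a proxy for age or sex, and the plan's risk-factor language with a significance rule encourages that reading.

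**Adjustment sets often belong in a separate SAP.** The protocol does not use the word unadjusted, and an SAP not shown here could add models. However, the section carries the title Statistical Analysis Plan and names the test for this comparison, so this is a stated choice. If another document does specify adjusted models, this text needs to be brought into line with it.

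**Every input to the size is assumed.** This stands in full. The ordinary cases give crude ORs of only 1.14 to 1.25, and the larger figures come from a deliberately strong case. Confounding by sex was not quantified.

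**Conclusion.** The concern holds. As planned, the ORs for binary complications are crude, and those for factors related to age or sex can be confounded where age or sex is also related to the complication. The point is conditional and its size cannot be derived from the protocol. In the continuous-age illustration, a factor with no association of its own shows a crude OR of 1.14 to 1.25 for a 5-year age gap and 1.56 in the strong 10-year case. There is no bias if either link is absent. This is a worthwhile and inexpensive improvement, and it does not invalidate the descriptive results.

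**What to change.** Add to the Statistical Analysis Plan section, before analysis, that each binary complication will also be analysed by logistic regression including age and sex, with adjusted ORs and 95% confidence intervals reported beside the crude ones. When age or sex is itself the factor of interest, the model adjusts for the other. Enter continuous risk factors as continuous terms. Keep the chi-square tests and crude ORs, labelled as descriptive. BMI, waist circumference, fat percentage and visceral fat rating overlap, so by default enter them one at a time and not together.

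The change takes one or two sentences and no new data. In the illustration, adjustment widens the standard error of the log OR by about 4 to 6% for a 5-year gap and 12% for a 10-year gap. When a complication is rare, the model can carry few covariates, so the plan should say that the set will then be kept small.
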